Amendment 01	11-Oct-2016	Addition of two unblinded interim analysis, addition of Sensory Motor Survey, clarification and updates to Eligibility criteria, and additional edits throughout the document to improve readability.
Original Protocol	28-Jun-2016	Not applicable

OVERALL RATIONALE FOR REVISED PROTOCOL 02:

These changes serve to clarify procedures for Part II Cohort 2 of the study. Part I Cohort 1 of the study is not impacted. Changes include:

SUMMARY OF KEY CHANGES FOR REVISED PROTOCOL 02		
Section Number & Title	Description of Change	Brief Rationale
Section 3.3.2 Exclusion Criteria	Exclusion criteria # 2b was modified to clarify: Suspected acute lung disease (eg, pneumonia or asthma) or severe chronic lung disease (eg, severe chronic obstructive pulmonary disease, pulmonary fibrosis, patients with hypercapnia or requiring home oxygen therapy or chronic oral steroids.)	Additional clarification for exclusion of patients with severe lung disease.
[REDACTED]	[REDACTED]	[REDACTED]
[REDACTED]	[REDACTED]	[REDACTED]

SUMMARY OF KEY CHANGES FOR REVISED PROTOCOL 02		
Section Number & Title	Description of Change	Brief Rationale
Section 3.1 Study Design and Duration	Changed to: Study Medication infusion must start within 18 hours of presentation (or 48 hours in Part II Cohort 2 of the trial), with presentation defined as the first dose of diuretic for current episode	[REDACTED]
Section 5.1.2 Treatment and In-Hospital Follow-up	Addition of window to collect vital signs within .25 hours of specified time points.	[REDACTED]
All	Minor formatting and typographical corrections	Minor, therefore have not been summarized

SYNOPSIS

Clinical Protocol CV013011

Protocol Title: A Multicenter, Randomized, Double-Blind, Parallel-Group, Placebo-Controlled, Dose-Ranging, Phase 2b Study of the Safety and Efficacy of Continuous 48-Hour Intravenous Infusions of BMS-986231 in Hospitalized Patients with Heart Failure and Impaired Systolic Function

Investigational Products, Dose and Mode of Administration, Duration of Treatment with Investigational Products: The investigational medicinal product is a solution for IV infusion containing BMS-986231 drug product (reconstituted in sterile water for injection), 5% dextrose (glucose) in water for injection (D5W) and potassium acetate (to achieve a 10 mM concentration of potassium acetate).

Study Phase: Phase 2B

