4.5 Selection and Timing of Dose for Each Subject

Subjects will be administered study medication as a continuous IV infusion over 48 hours.

Body weight measured at screening will be used for dose calculations.

Every effort must be made to initiate study drug administration promptly after randomization.

See Pharmacy Manual for additional dosing information.

4.5.1 Dose Reductions, Temporary Interruptions, and Permanent Discontinuations of Study Drug Due to Blood Pressure

Any decision to lower the dosage level of study drug or discontinue study drug should be based on the Investigators assessment of the subject's overall clinical stability, in the context of appropriate ongoing monitoring of the subject's condition. A 50% dosage adjustment downward maybe be achieved by decreasing the rate of study drug infusion.

In Part I (Cohort 1) subjects who require a dose reduction or temporary interruption during the first infusion period, hours 0 to 4 (dose of 3 µg/kg/min), will be permanently discontinued from study drug.

Study drug infusion rate may be reduced by 50%, temporarily interrupted, or permanently discontinued. See [Figure 4.5.1-1](#) and the following sections for more detail.

Dose Reduction:

- If the subject experiences SBP < 95 mm Hg, without symptoms related to hypotension, the measurement must be repeated within 15 minutes. If the SBP remains < 95 mm Hg, the dose reduction must occur
- A 50% dosage adjustment downward may be achieved by decreasing the rate of study drug infusion by half
- After a dose reduction, the dose cannot be increased again

Temporary interruption:

- If the systolic blood pressure reduces below < 85 mm Hg, and remains < 85 mm Hg during a repeated measure within 15 minutes, the study drug must be interrupted for at least 1 hour
- For subjects that report symptoms consistent with hypotension (eg, dizziness, lightheadedness, etc.), and are related to hypotension, study drug must be interrupted for at least 1 hour

[figure not shown]
Resuming Study Drug

- Study drug may be resumed at 50% of the dose after 1 hour interruption, if SBP rises to values ≥ 105 mm Hg and any symptoms of hypotension, if present, have resolved.
- If after 4 hours, the subject’s SBP remains below < 105 mm Hg, or if symptoms persist, then study drug must be permanently discontinued
- After a dose reduction, the dose cannot be increased again

Permanent discontinuation of the infusion:

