Central Laboratory Assessments			See Section 5.3.5.2 for Analytes
Hematology and Serum Chemistry		X	
Hs Troponin T		X	
NT-proBNP, Serum Cystatin C, NGAL		X	
CRP		X	
Urinalysis		X	
Urine creatinine, Na ⁺ , and K ⁺		X	
Efficacy Assessments			
Resting Dyspnea measured by the Numerical Rating Scale (NRS) ^a		X	
Other Assessments			
Sensory Motor Survey		X	

^a If subject is receiving supplemental oxygen, perform NRS without removing oxygen

Table 5.1-2: Treatment and In-Hospital Follow-up (CV013011)

Procedure	Hour 0-23 ^a (Post Rand, Day 1)	Hour 24 ± 2	Hour 48 ± 2	Hour 72 ± 2	Hour 96 ± 2	Hour 120 ± 2 or Discharge ^{b c}	Notes (Time is relative to start of dosing)
Randomize Subject	X						Randomization must take place before Hour 0
Administer Study Medication		X					48 hour continuous infusion *Study medication infusion begin promptly after randomization*
Safety Assessments							
Body Weight		X	X	X	X	X	
Vital Signs: Blood Pressure and Heart Rate ^d	X	X	X	X	X	X	Perform Semi-Recumbent (at a 30° angle) Day 1: Hours 0, 0.5, 1, 2, 4, 5*, 6, 8, 9*, 10, 12, 14, 16, 18, 20, 22 Hours: 24, 28, 32, 36, 40, 44 Hours 48, 54, 60, 66 Hour 72 Hour 96 Hour 120 Perform measurements before IV bag change, when possible. Repeats as per Section 5.3.1 Perform also if signs or symptoms of hypotension *Part I (Cohort 1) only
Respiratory Rate	X	X	X	X	X	X	Day 1: Hours 6 and 12
Use of Oxygen Supplementation, Oxygen Saturation	X	X	X	X	X	X	Day 1: Hours 6 and 12

Table 5.1-2: Treatment and In-Hospital Follow-up (CV013011)

Procedure	Hour 0-23 ^a (Post Rand, Day 1)	Hour 24 ± 2	Hour 48 ± 2	Hour 72 ± 2	Hour 96 ± 2	Hour 120 ± 2 or Discharge ^{b c}	Notes (Time is relative to start of dosing)
Temperature		X	X	X	X	X	
12-Lead ECG		X	X	X		X	
Telemetry Monitoring	X						Continuous monitoring through Hour 50
Holter Monitoring (Part II Cohort 2 Only)		X					For participating sites. Continuous monitoring through Hour 52. 12-lead ECGs will be extracted at 3 timepoints prior to the start of the infusion and at the same timepoints as PK determinations up to and including 48 hours post-dose (See section 5.5) Subjects will be supinely resting in a semi-recumbent position for at least 10 minutes prior to and 5 minutes after each timepoint for ECG extraction (Day 1: Hour 0.75, 4*, 8*, 14, 48 and Hour 52). When ECG extractions coincide with 12-lead safety ECGs, blood draws and other assessments, ECG extractions should, when feasible, be performed in said order.

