5.3.1 Assessment of Blood Pressure and Symptoms for Hypotension

The primary endpoint of the study is the incidence of clinically relevant hypotension, defined by SBP < 90 mm Hg (confirmed by a repeated value < 90 mm Hg) or symptoms of hypotension, up to 6 hours after the end of study drug infusion. Thus hypotension will be assessed by collection of symptoms and blood pressure measurements.

Symptomatic hypotension is defined as the presence of both low SBP and significant and/or non-resolving symptoms due to low blood pressure (eg, lightheadedness, dizziness, etc.).

Blood pressure measurements should be performed with the subject in a semi-recumbent (about a 30° angle) position, whenever possible.

Blood pressure will be measured as indicated in Table 5.1-2, within (± 0.25) of the specified time points. In addition, sites may perform measurements at intervals defined by institutional standard of care for subjects receiving vasodilators, but no less than what is described in Table 5.1-2.

If the study drug dose is modified (decreased, interrupted, resumed or discontinued) the frequency of blood pressure measurements will follow a more intensive schedule for up to 6 hours following the dose modification (Table 5.3.1-1). Upon completion of the intensive schedule, measurements can be either resumed per the original schedule, or follow the discontinuation schedule if the drug is permanently discontinued.

Table 5.3.1-1: Schedule of Intensive Blood Pressure Collection Following a Dose Modification

	30 minutes post	1 hour post	2 hours Post	4 hours post	6 hours post
Dose reduction	X	X	X	X	X
Dose interruption ^a	X	X	X	X	
Dose resumption ^b	X	X	X	X	X
Dose discontinuation	X	X	X	X	X ^c

^a dose must be resumed within 4 hours of dose interruption. If interruption last beyond 4 hours, dose must be discontinued and discontinuation schedule must be followed.

^b If dose is restarted within 4 hours following interruption, follow schedule for dose resumption

^c After 6 hours, continue collecting blood pressure measurement at a minimum of every 12 hours through hour 72 or follow the local institutional standard of care protocol, whichever is more frequent.

In addition to assessments of blood pressure, the Investigator will be asked to collect and assess signs and symptoms of low blood pressure The details to be captured will include:

- Onset date/time
- Total duration of episode
- Lowest blood pressure during the episode

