Central Laboratory Assessments			See Section 5.3.5.2 for Analytes
Hematology and Serum Chemistry		X	
Hs Troponin T		X	
NT-proBNP, Serum Cystatin C, NGAL		X	
CRP		X	
Urinalysis		X	
Urine creatinine, Na+, and K+		X	
Efficacy Assessments			
Resting Dyspnea measured by the Numerical Rating Scale (NRS) ^a		X	
Other Assessments			
Sensory Motor Survey		X	

^a If subject is receiving supplemental oxygen, perform NRS without removing oxygen

Table 5.1-2: Treatment and In-Hospital Follow-up (CV013011)

Procedure	Hour 0-23 ^a (Post Rand, Day 1)	Hour 24 ± 2	Hour 48 ± 2	Hour 72 ± 2	Hour 96 ± 2	Hour 120 ± 2 or Discharge ^{b c}	Notes (Time is relative to start of dosing)
Randomize Subject	X						Randomization must take place before Hour 0
Administer Study Medication		X					48 hour continuous infusion *Study medication infusion begin promptly after randomization*
Safety Assessments							
Body Weight		X	X	X	X	X	
Vital Signs: Blood Pressure and Heart Rate ^d	X	X	X	X	X	X	Perform Semi-Recumbent (at a 30° angle) Day 1: Hours 0, 0.25 (15 min), 0.5 (30 min), 0.75 (45 min), 1, 1.5, 2, 4, 5* , 6, 8, 9* , 10, 12, 14, 16, 18, 20, 22 Hours: 24, 28, 32, 36, 40, 44 Hours 48, 54, 60, 66 Hour 72 Hour 96 Hour 120 Perform measurements before IV bag change, when possible. Repeats as per Section 5.3.1 Perform also if signs or symptoms of hypotension *Part I (Cohort 1) only
Respiratory Rate	X	X	X	X	X	X	Day 1: Hours 6 and 12
Use of Oxygen Supplementation,	X	X	X	X	X	X	Day 1: Hours 6 and 12

Table 5.1-2: Treatment and In-Hospital Follow-up (CV013011)

Procedure	Hour 0-23 ^a (Post Rand, Day 1)	Hour 24 ± 2	Hour 48 ± 2	Hour 72 ± 2	Hour 96 ± 2	Hour 120 ± 2 or Discharge ^{b c}	Notes (Time is relative to start of dosing)
Oxygen Saturation							
Temperature		X	X	X	X	X	
12-Lead ECG		X	X	X		X	
Telemetry Monitoring	X						Continuous monitoring through Hour 50

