Pharmacokinetic Blood Samples Collection and Preparation of Blood Samples	X		X	X			Part I Cohort 1: Day 1: Hour 0.75, 4, 8, 14 Hour 48 Hour 52 Part II Cohort 2: Day 1: Hour 0.75, 6, 14 Hour 48 Hour 52 Perform measurements before IV bag change or stopping the infusion, whenever possible. Collect sample when dose lowered due to a safety event and also at time of early discontinuation of study drug.

Table 5.1-2: Treatment and In-Hospital Follow-up (CV013011)

Procedure	Hour 0-23 ^a (Post Rand, Day 1)	Hour 24 ± 2	Hour 48 ± 2	Hour 72 ± 2	Hour 96 ± 2	Hour 120 ± 2 or Discharge ^{b c}	Notes (Time is relative to start of dosing)
Efficacy Assessments							
Resting Dyspnea measured by Numerical Rating Scale (NRS) ^e	X	X	X	X		X	Day 1: Hours 6 and 12
Resting Dyspnea measured by 7-point Likert Scale ^e	X	X	X	X		X	Day 1: Hours 6 and 12
Patient Global Assessment measured by 7-point Likert Scale ^e	X	X	X	X		X	Day 1: Hours 6 and 12
Assessments of Worsening Heart Failure		X	X	X	X	X	Documentation of Worsening Physical Signs and Symptoms of Heart Failure, and Documentation of Initiation or Increased dose of Parenteral Diuretic, Vasodilator and/or Inotropes, or Need for Mechanical interventions (mechanical ventilation, circulatory support, ultrafiltration or dialysis). Assessments to cover prior 24 hour period.
Wristworn Actigraphy monitoring device (watch) (Part II Cohort 2)			X	X	X	X	For participating sites. Provide the device to subjects at the end of the 48 hours infusion or when the study drug has been permanently discontinued
Other Assessments							
Sensory Motor Survey						X	

^a Hour 0 defined as start of study medication infusion

- b Visit to occur at Hour 120 \pm 2 or Discharge, whichever comes first. If subject is discharged after Hour 120, no further protocol in-hospital visits are completed
- c Assessments required at Discharge Visit should not be repeated if performed within previous 12 hours
- d Vital signs should be taken within (\pm 0.25)
- e If subject is receiving supplemental oxygen, perform NRS without removing oxygen

Table 5.1-3: Outpatient Follow-up (CV013011)

[figure not shown]
Procedure	Day 32 (± 2 Days) Clinic Visit ^a	Day 182 (± 5 Days) Phone Visit ^b	Notes
Safety Assessments			
Vital Signs: Blood Pressure and Heart Rate	X		When possible, perform Semi-Recumbent (at a 30° angle)
Respiratory Rate	X		
Body Weight	X		
Temperature	X		
Serious Adverse Events Assessment	X		
Local Laboratory Assessments			

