8.3 Endpoints

8.3.1 Primary Endpoint

The primary endpoint is the incidence of clinically relevant hypotension, defined by SBP < 90 mm Hg (confirmed by a repeated value < 90 mm Hg) or symptoms of hypotension, up to 6 hours after the end of study drug infusion.

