8 CONVENTIONS

8.1 Safety Data Conventions

Except as noted in [Section 7.6](#), safety data will be handled according to the BMS safety data conventions. This document includes descriptions on how to analyze AE data as well as how to handle partial dates, missing dates, and unknown end dates when analyzing safety data. If onset time of AEs is missing or incomplete, the onset date of AEs will be used to determine if the AEs will be included in the AE summary tables as follows.

- Non-serious AEs will be included in summary tables if the onset date is on or after the start date of study treatment and not later than the date of Hour 120.
- Serious AEs will be included in summary tables if the onset date is on or after the start date of study treatment and not later than the date of Day 32.

Clinically relevant hypotension defined in the primary endpoint consists of two components which are further clarified as follow:

- The component of “SBP < 90 mm Hg (confirmed by a repeated value < 90 mm Hg)” will be identified by a SBP measurement < 90 mm Hg with confirmatory SBP measurement < 90 mm Hg within 30 minutes after the initial qualifying value. If a confirmatory SBP is missing, the initial SBP will be treated as confirmed if no SBP measurement \geq 90 mm Hg within 30 minutes exists. The assessment time of the initial SBP < 90 mm Hg will include time from start of infusion, up to and including 6 hours after end of infusion.

The confirmatory measurement should be within 15 minutes; however, a window of up to 30 minutes will be applied, to determine if a qualifying confirmatory value is obtained.

- The component of “symptoms of hypotension” will be identified by at least one symptom (other than “low blood pressure”) from the CRF page collecting signs and symptoms of low blood pressure with onset time from start of infusion, up to and including 6 hours after end of infusion

This clarification is also applied to the safety endpoints “The incidence of symptomatic hypotension up to 6 hours after the end of study drug infusion, as well as the incidence of SBP < 90 mm Hg (confirmed by a repeated value)”.

Subjects counted in the endpoint “Percentage of subjects with discontinuation due to symptomatic hypotension” are those who have “Hypotension” as the reason for discontinuation and have a symptom (other than “low blood pressure”) from the CRF page collecting signs and symptoms of low blood pressure with onset time on or before the time of dose discontinuation.

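### SAP 8.1 ends the primary endpoint window exactly at the planned Hour 54 blood pressure reading, without the 15-minute tolerance the protocol gives that reading

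*SAP*

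**What the plan says.** Protocol 8.3.1 defines the primary endpoint as a confirmed SBP below 90 mm Hg "or symptoms of hypotension, up to 6 hours after the end of study drug infusion". SAP 8.1 makes this operational: the first low value must be timed between the start of infusion and "up to and including 6 hours after end of infusion". The confirming value may follow within 30 minutes, which the SAP presents as a widening of an expected 15 minutes. The first value gets no such allowance.

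Protocol 4.5 fixes the planned infusion length: "Subjects will be administered study medication as a continuous IV infusion over 48 hours". Table 5.1-2 schedules blood pressure at "Hours 48, 54, 60, 66" and then at Hours 72, 96 and 120, with the note "Time is relative to start of dosing". Protocol 5.3.1 asks for measurement "within (± 0.25) of the specified time points", and footnote d of Table 5.1-2 repeats the 0.25. The summary of changes for Revised Protocol 02 dates this and gives the unit: "Addition of window to collect vital signs within .25 hours of specified time points". The same summary says Part I is not affected. Revised Protocol 02c keeps 15 minutes at Hour 54 and narrows the tolerance only in the first hour.

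SAP 2.4 states that the SAP rests on Revised Protocol 01. SAP 8.3 assigns vital signs to nominal times by midpoints, but does not link this to the primary endpoint.

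**The concern.** For completers, the planned observation of the six hours after infusion comes down to one reading, at Hour 54, and the endpoint window closes at that same moment. The protocol accepts the reading at any time from 53:45 to 54:15. The SAP accepts it only up to six hours after the actual end of infusion. A reading at 54:05 after an infusion that ended at 48:00 complies with the protocol, would be tabulated as Hour 54 among the vital signs, and would not count toward the primary safety endpoint.

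The two clocks also start from different points: the reading from the start of dosing, the cut-off from the end of infusion. An infusion that ends a few minutes early or late therefore changes whether the reading counts.

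What is at stake is ascertainment of the primary safety event. Against a rule that counts the nominal reading, the present rule can only lose events, and it does so on minutes of charting that have no clinical meaning.

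**Working it through.** **Inputs**

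- Cut-off for the first low SBP: end of infusion + 6 h, inclusive (SAP 8.1).
- Planned end of infusion: 48:00 (Protocol 4.5), so the nominal cut-off is 54:00.
- Planned readings: Hours 48, 54, 60 and 66, timed from start of dosing (Protocol Table 5.1-2).
- Tolerance: 15 minutes either side (Protocol 5.3.1 and Table 5.1-2, footnote d).
- Part II group size: about 70 (Protocol 8.1).

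**The plan's own figures.** The documents give no share of Hour 54 readings lost. The design figures tied to this endpoint are the probabilities for the sample decision rules in Protocol 8.1. For Part II I enumerated two independent binomials with 70 per group, an observed ratio above 1.8 and a difference above 3 points. Detection is 81.7% (5% vs 15%) and 79.7% (10% vs 25%); false detection is 15.2% and 12.7%. The protocol states 82%, 80% and 13-15%, so these reproduce. They take event rates as given and do not involve the Hour 54 rule.

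**Share of compliant readings excluded.** Let *r* be the minutes by which the reading departs from 54:00 (-15 to +15), and *e* the minutes by which the infusion end departs from 48:00. The reading is excluded when *r* > *e*. If *r* is uniform, P(*r* > *e*) = (15 - *e*)/30.

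| Infusion ends | e | Share excluded |
|---|---|---|
| 47:45 | -15 | 30/30 = 100% |
| 47:55 | -5 | 20/30 = 67% |
| 48:00 | 0 | 15/30 = 50% |
| 48:05 | +5 | 10/30 = 33% |
| 48:10 | +10 | 5/30 = 17% |
| 48:15 or later | +15 or more | 0% |

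With the infusion ending at 48:00 and other assumed reading times:

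- Whole-minute recording, uniform: 15/31 = 48%.
- 60% charted at exactly 54:00, the rest uniform: 0.4 x 0.5 = 20%.
- Triangular, mode 5 minutes early: 38%; mode 5 minutes late: 63%.

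**Treatment in SAP 8.3.** The midpoints are (48 + 54)/2 = 51 and (54 + 60)/2 = 57. The Hour 54 range is therefore from Hour 51 to before Hour 57, and it contains every compliant reading.

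**Which subjects could change.** The endpoint counts subjects with at least one event (SAP 7.6.1). A subject is lost only if the first qualifying low SBP is at a late Hour 54 reading, with no earlier confirmed low value, no symptom onset inside the window, and no unscheduled low reading inside it. Hour 54 is 1 of 22 readings planned from Hour 0 to Hour 54 in Part II (1 of 25 under Revised Protocol 02c).

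**Size.** One event is 1/70 = 1.4 points of a Part II arm rate. Planned placebo events over the whole window are 0.05 x 70 = 3.5 to 0.10 x 70 = 7; how many would first appear at Hour 54 is not given. As an illustration only, suppose 5% of events were lost in both arms. With the ratio condition read as at least 1.8, detection would move from 83.4% to 82.4% (5% vs 15%) and from 80.6% to 79.9% (10% vs 25%).

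**The case against.** The strongest reply is that the SAP follows the protocol. The endpoint is defined up to six hours after infusion, so a first low value at 6 h 05 min lies outside it, and excluding it is not an error. Read literally, that is right. It does not remove the difficulty, because the schedule puts the planned reading on the boundary and lets half of its permitted interval fall beyond the nominal cut-off. The same section of the SAP gives the confirmatory value a tolerance, and SAP 8.3 treats the late reading as Hour 54.

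Several stronger readings are tempting, and the documents do not support them:

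- **Half of compliant readings are lost.** This needs an infusion end at exactly 48:00, times symmetric about 54:00, and few readings charted at exactly 54:00. No document gives any of these.
- **Hour 54 is the only reading after infusion.** Hours 60, 66, 72, 96 and 120 follow. An Hour 48 reading taken slightly late could also fall after infusion ends, although Table 5.1-2 asks for readings before a bag change when possible.
- **Early discontinuers have the same problem.** They are read at 0.5, 1, 2 and 4 hours, well inside the window. Only their 6-hour reading is on the boundary, and Table 5.3.1-1 states no tolerance for it.
- **Both parts are equally affected.** The tolerance came with Revised Protocol 02, which says Part I is not impacted.

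It also stands that the rule is the same in every arm, that readings prompted by symptoms are required as well, and that Protocol 6.5 reports blood pressure recovering within 1-2 hours of stopping in earlier studies.

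**Conclusion.** The point holds as a narrow mismatch between the SAP's cut-off and the protocol's measurement tolerance, mainly in Part II. For completers, the one reading planned after Hour 48 and inside the primary window can comply with the protocol and still be excluded. The share is unknown: the 50% and 20% figures rest on assumed timing, and modest shifts in infusion end span 0% to 100%.

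A reader might infer that the primary result is materially biased. The documents do not show that. Few events are likely to change, each is worth about 1.4 points of a Part II arm rate, and no stated design figure or decision rule depends on the point. The SAP's basis in Revised Protocol 01 suggests that it was not updated when the tolerance was added. This is a minor correction, worth making because it concerns the primary safety endpoint and costs almost nothing.

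**What to change.** In SAP 8.1, count an initial SBP below 90 mm Hg at the nominal Hour 54 reading whenever that reading is taken within its protocol tolerance. Apply this to the SBP component of the primary endpoint and to the separate endpoint of confirmed SBP below 90. Leave the symptom-onset window unchanged, since onset is not tied to a scheduled reading.

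For early discontinuers, state whether the same tolerance applies to the 6-hour reading after discontinuation.

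Tying the rule to the nominal reading is better than moving the cut-off to 6 h 15 min. If infusion ended at 47:55, that cut-off would fall at 54:10 and still drop a compliant reading at 54:12.

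The cost is one or two sentences, settled before treatment codes are seen. The downside is that a value up to 15 minutes beyond the literal six hours may count when infusion ends at 48:00, and slightly more when it ends early (47:55 to 54:15 is 6 h 20 min). The SAP should describe this as a measurement convention so that the departure from the literal protocol window is visible.
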